5.3.3 Central Laboratory Assessments

Blood/Urine Standard Safety Panel and Urine pregnancy tests- Refer to Appendix 2 for details.

Protocol Specific Tests:

7-point central lab glucose monitoring will be performed before and 2-hr after each meal [breakfast, lunch, dinner] as well as bedtime[~11 pm])- see central lab manual for details

MB102072

- 24 hour urinary glucose and percent inhibition of renal glucose reabsorption- see Appendix 2 for formula
- FPG
- Fasting C-Peptide •
- Serum insulin .
- A1C .
- Hepatitis Screen Panel/TSH •
- Fasting Serum Lipids •
- FFA •
- Serum β -hydroxybutyrate •
- 24 -hour urine collection Urine will be collected over a 24-hour period on days -1, 1 • and 7 for assessment of glucose, sodium, uric acid and creatinine. In the morning, on the day that the 24-h urine collection is started, the first morning void is not included in the 24-h collection. The date and time of the first urine should be recorded on the urine collection log as the start of the 24-h urine collection. All subsequent urinations throughout the entire day and night, and into the following day should be collected. The first voided urine of the subsequent day should be included in the 24-hr urine collection. The urine collection ends after 24 hrs and the stop time should equal the start time of the previous day. The stop date and time should be recorded on the urine collection log.

5.3.4 Urine ketone testing

The site will use Ketostix® () for urine ketone testing during the inpatient component of the study, and provide each subject with sufficient supplies of Ketostix® for urine ketone testing during the outpatient component of the study. Urine ketone testing will be performed according to the manufacturer's specifications and the subject should be trained in the procedure during the initial inpatient period. Urine ketone testing will be performed daily in the morning (shortly after arising, and fasted) and anytime the subject has symptoms suggestive of ketoacidosis or a fingerstick blood glucose in excess of 250 mg/dL. Results should be recorded in the subject diary/ePRO device. Results read from the color chart are 'Negative', 'Trace' (5 mg/dL), 'Small' (15 mg/dL), 'Moderate'

dapagliflozin	MB102072
BMS-512148	Clinical Protocol

(40 mg/dL), and 'Large' (80 - 160 mg/dL). The subject should contact the site for assistance with diabetes management in the event that a result of 'Moderate' or 'Large' is obtained.

5.3.5 Fluid intake/output

Fluid intake/output (24 hour) will be collected during the inpatient stay as indicated and captured on the eCRF.

5.3.6 Insulin Dosing Assessment and Adjustment Guidelines

Adjustment of a subject's pre-existing insulin dosing regimen may be required during the conduct of this study, due to changes in diet, activity, emotional stress during the study as well as potential effects of dapagliflozin to reduce blood glucose and thereby insulin requirements. Because this is a short-term study, the primary goal for insulin adjustment is to avoid significant hyperglycemia or hypoglycemia, rather than strict glycemic control. Insulin adjustment should not be performed to 'fine tune' glycemic control, but rather to ensure patient safety in the event that there is a significant change in insulin requirements. Maintaining the majority of blood glucose readings between 70 - 220 mg/dL is considered adequate glycemic control for subjects during the course of this study. In general, the goal would be to maintain fasting blood glucose between 70 - 140 mg/dL and postprandial blood glucose below 220 mg/dL, although these goals may be individualized based upon a specific subject's personal targets and stability of glycemic control at baseline.

The two main scenarios in which insulin adjustment is appropriate are unexpected events of either hypoglycemia or hyperglycemia. An unexpected event is defined as an event that cannot be explained by circumstances such as dietary (missed or unusually high carbohydrate meal), strenuous exercise, error in insulin dosing, etc. In subjects with one or more unexpected events of hypoglycemia or hyperglycemia, insulin dosing should be adjusted.

In the event insulin dose adjustment is deemed necessary, the investigator should guide insulin dose changes, based upon review of the insulin and glucose logs, as well as potential circumstances that may have contributed to erratic glucose control (e.g. insulin dosing errors, missed meals, unusual physical activity, etc). In addition, consultation with the subject and/or appropriate representatives of the subject's diabetes management team

dapagliflozin	MB102072
BMS-512148	Clinical Protocol

is strongly recommended. The BMS Medical Monitor is also available to assist with insulin dose adjustment. Subjects should be instructed to contact the site for insulin dose adjustment instructions in the event they are experiencing poor glycemic control or have unexpected events of hypoglycemia or hyperglycemia.

As dapagliflozin has not been studied previously in T1DM, it is difficult to predict the impact upon glycemic control and insulin requirements in this population. Given the half-life of dapagliflozin of approximately 12 hours and the duration of pharmacodynamic activity of approximately 24 hours, basal insulin requirements may be reduced. In addition, the amount of glucose excreted in response to dapagliflozin is dependent upon the filtered glucose load, which reflects the plasma glucose concentration (and glomerular filtration rate). Therefore, reductions in bolus insulin may also be required. A reduction in both basal and bolus insulin commensurate with the proportion of each insulin a subject receives may be an appropriate first approach, with individualization for each subject based upon the results of glucose monitoring.

5.3.7 Diet/Exercise

Starting at Day -3 visit and for the duration of the study, subjects will be instructed on a diet and exercise program in accordance with the ADA (or similar local guidelines).

A Registered Dietitian, Registered Nurse, Physician, Certified Diabetes Educator, Nutritionist, or other qualified member of the study team who has appropriate documented training will provide this counseling.

The meals provided during the inpatient portion of the study should provide appropriate caloric intake for a weight-maintaining diet. During the inpatient period, the subjects should not be allowed foods from outside the clinic or additional snacks, except for the treatment of hypoglycemia.

5.3.8 Physical Examination (PE), ECG, Blood Pressure, Heart Rate

PE

A brief physical examination should include cardiovascular, lungs, abdomen, and extremities, and any organ systems pertinent to the subject's signs, symptoms, or adverse events

dapagliflozin	MB102072
BMS-512148	Clinical Protocol

A complete physical examination should include general appearance, head, eyes, ears, nose, throat, neck, cardiovascular, lungs, abdomen, lymph nodes, extremities, neurological, skin, genitourinary, and musculoskeletal.

The individual performing the physical examinations must be licensed by state law (or applicable local law) to perform this procedure.

ECG

ECGs will be performed at Screening and Day 14/ET visits.

The Investigator should review and assess all ECGs for any clinically significant abnormalities, and initial and date the report. The screening ECG must be assessed, and initialed and dated by the Investigator prior to randomizing the subject.

In preparation for the ECG, ensure there is minimal interference between the skin surface and the electrode. Use alcohol to prepare the skin at each electrode site. Thick chest hair should be shaved to ensure sufficient contact.

Before attaching electrodes to pick-up points, spread the electrode with electrode gel. Place the electrodes on bony areas, avoiding large muscle masses, to achieve better tracings as described below. The subject must be supine and should refrain from movement during the ECG recording. Ensure that the subject and the electrodes (including the neutral electrode) are not exposed to conducting objects, even if grounded.

- RL: On the right leg (inside calf, midway between knee and ankle)
- LL: On the left leg (inside calf, midway between knee and ankle)
- RA: Right arm (on the inside)
- LA: Left arm (on the inside)
- V1: 4th intercostal space, at right sternal margin
- V2: 4th intercostal space, at left sternal margin
- V3: Midway between V2 and V4
- V4: 5th intercostal space at left midclavicular line
- V5: Same transverse level at V4, at anterior axillary line
- V6: Same transverse level at V4, at left midaxillary line

dapagliflozin	MB102072
BMS-512148	Clinical Protocol

Keep one original ECG print-out in the medical chart and ensure a copy, assessed, initialed and dated by the Investigator, is maintained in the source documents for the study.

Blood Pressure (BP) and Heart Rate (HR)

BP and HR measurements must be taken consistently as indicated throughout the study. Blood pressure measurements using a calibrated mercury sphygmomanometer throughout the study are preferred. If possible, blood pressure measurements should be taken by the same person, with the same device, throughout the study.

All measurements should occur at least 10 hours after the last ingestion of caffeine, alcohol, or nicotine. Only use either the right or the left arm when measuring these parameters. At the randomization visit, it is crucial that the blood pressure measurement and heart rate be obtained prior to the first dose of blinded study medication.

Seated BP

The subject should be allowed at least 5 minutes of rest before measurement. Seated blood pressure should be measured with the subject's arm resting on a table, and with subject's back supported and feet flat on the floor.

Seated BP and HR will be determined from three replicate measurements obtained at least 1 minute apart. The average BP and HR will be determined from these 3 replicate measurements and reported in the eCRF.

Orthostatic BP

Orthostatic measurements should be obtained following completion of seated BP and heart rate and prior to administration of study medication. The subject should rest in the supine position for at least 5 minutes prior to measurement of BP and HR. Supine BP will be determined from three replicate measurements obtained at least 1 minute apart. The average BP and HR will be determined from these 3 replicate measurements and reported in the eCRF.

The subject will then stand for 2 to 3 minutes. After this time, measure the BP with the arm supported at the antecubital fossa at heart level. Standing BP and HR will be determined from 3 replicate measurements obtained at least 1 minute apart. The average

dapagliflozin	MB102072
BMS-512148	Clinical Protocol

BP and HR will be determined from these three replicate measurements and reported in the eCRF.

5.3.9 Guidance on Assessment of Urinary and Genital Infections

The following is presented to assist in the classification and management of urinary tract and genital infections. It is not intended to supplant investigators' clinical judgment:

Asymptomatic bacteriuria is defined as the presence of $\ge 10^5$ colony forming units/mL of bacteria, in a properly collected voided urine specimen, without signs or symptoms typically attributed to urinary tract infection. Asymptomatic bacteriuria is prevalent among diabetic women, and is associated with pyuria in 70% of cases.¹ Neither the Infectious Diseases Society of America nor the U.S. Preventive Services Task Force recommends screening for, or treatment of, asymptomatic bacteriuria in non-pregnant diabetic patients.^{1, 2} In this study, the central laboratory will not routinely report the results of urinary dipstick tests for leukocyte esterase as a screening test for pyuria in surveillance urine examinations.

At every scheduled visit, the Investigator will question subjects about symptoms of **urinary tract infections**, including but not limited to pain or burning or uncomfortable pressure in the lower abdomen/pelvic area while passing urine, blood in the urine, and symptoms of urinary urgency (a strong and uncontrolled urge to pass urine). If based on the response to these questions or other suggestive signs or symptoms the investigator believes that a urinary tract infection may be present, local laboratory urine cultures **must** be obtained to confirm a presumptive diagnosis of cystitis, urinary tract infection, or pyelonephritis. Mid-stream clean catch urine collections are recommended. Clinical judgment and local standards of care should apply to decisions concerning therapy.

Study drug should be held in subjects with clinical evidence of upper tract UTI (eg pyelonephritis) or presumed urosepsis until the course of treatment of the infection has been completed and clinical recovery has occurred.

It is recommended that a follow-up urine culture be obtained within 7 days of clinical recovery from all urinary tract infections. Whether or not additional therapy is prescribed because of culture results should be determined by Investigator judgment, after consultation with the Medical Monitor.

In addition, at every scheduled study visit, the investigator will question subjects about symptoms of **genital infections** including but not limited to itching, soreness or redness in the genital area and a change or increase in genital discharge. The diagnosis of vaginitis, vulvovaginitis, vulvitis or balanitis can be made based on physical examinations, culture of secretions or a therapeutic response to treatment of fungal or other vaginal pathogens. A urine culture is not required for diagnosis of genital infections.

Guidance on Assessment of Hematuria

In the event that hematuria is observed during a subject's participation, the Sponsor recommends standard of care in diagnosing the cause of the hematuria.

It is the investigator's responsibility to report, as applicable based on Investigator's judgment and subject's medical history, related adverse events as defined in Section 6.0. Additional information, including but not limited to completion of supplemental eCRFs may be requested for certain adverse events and/or laboratory abnormalities which are reported/identified during the course of the study.

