1.5 Overall Risk/Benefit Assessment

This protocol includes an experimental compound, dapagliflozin, being developed as a potential new therapy for hyperglycemia in subjects with type 2 diabetes. Dapagliflozin has been effective at lowering glucose and A1C in subjects with T2DM, when studied as monotherapy as well as in combination with insulin or oral anti-diabetic medications. Dapagliflozin has not previously been studied in subjects with type 1 diabetes. Because subjects with T1DM are absolutely insulin deficient, insulin treatment is required for survival and dapagliflozin would not be a replacement for insulin therapy. However, dapagliflozin reduces glucose by an insulin-independent mechanism (reduction of glucose reabsorption by the kidney, leading to glucose loss in the urine) and potentially may be effective in improving glycemic control in subjects with T1DM when used in combination with insulin.

As noted above, dapagliflozin was generally safe and well-tolerated in completed clinical studies in subjects with T2DM. Overall, the frequency of genital and urinary tract infections was higher in subjects treated with dapagliflozin and a small dose-dependent increase in hematocrit was observed in dapagliflozin treated subjects without any associated clinically relevant events.

In this pilot study in T1DM, the doses of dapagliflozin have been chosen to span the range of doses studied in the Phase 3 program in subjects with T2DM. It is expected that the safety and efficacy profile in subjects with T1DM will be similar to that observed in

dapagliflozin	MB102072
BMS-512148	Clinical Protocol

subjects with T2DM. However, improvement in glucose control may result in an increased risk of hypoglycemia from concomitant insulin treatment. Therefore, dapagliflozin will be started in an inpatient setting to allow for careful insulin adjustment and to optimize safety monitoring.

Additional clinical safety and efficacy information is available in the Investigator Brochure.

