3.5.2 Discontinuation Guidelines due to sustained elevated Serum Creatinine

Subjects will have double blind study medication withheld and a confirmatory, repeat S_{Cr} drawn within one week, if the following criterion is met:

• Male or female subjects: $S_{Cr} \ge 2.0 \text{ mg/dL} (176 \mu \text{mol/L})$

The following actions should be taken upon receipt of the central laboratory repeat SCr result:

- If the repeat S_{Cr} is < 2.0 mg/dL (176 μ mol/L), double-blind study medication may be resumed unless otherwise contraindicated.
- If the repeat S_{Cr} is $\geq 2.0 \text{ mg/dL}$ (176 μ mol/L), the subject must be immediately discontinued from the study, the Sponsor notified, and the Day 14 visit performed. The Investigator will follow the subject until the event has resolved or stabilized.

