3.5.4 Discontinuation Guidelines due to Hyponatremia

Subjects with a serum sodium $\leq 125 \text{ mEq/L} (125 \text{ mmol/L})$ will have double-blind study medication withheld and a confirmatory, repeat serum sodium, drawn within 3 days following receipt of the initial laboratory result.

- If the repeat serum sodium is $\geq 130 \text{ mEq/L} (130 \text{ mmol/L})$:
 - Double-blind study medication may be resumed unless otherwise contraindicated.
 - Serum sodium should be re-tested within one week after resuming the double blind study medication.
 - If the repeat of serum sodium, obtained within one week after resuming double-blind study medication, is < 130 mEq/L (130 mmol/L), the subject must be immediately discontinued from the study, the Sponsor notified and the Day 14/ET visit performed. The Investigator will follow the subject until the event has resolved or stabilized.
 - If the repeat of serum sodium, obtained within one week after resuming double-blind study medication, is ≥ 130 mEq/L (130 mmol/L), the subject may continue in the study and will be followed according to the protocol. Additional monitoring of serum sodium may be performed according to the local practice or Investigator's judgment.
- If the repeat serum sodium is < 130 mEq/L (130 mmol/L) **AND** there is no suspected new, temporary and reversible cause of hyponatremia based on clinical assessment (other than the administration of double-blind study medication), the subject must be immediately discontinued from the study, the Sponsor notified and the Day 14/ET visit performed. The Investigator will follow the subject until the event has resolved or stabilized.
- If the repeat serum sodium is < 130 mEq/L (130 mmol/L) **AND** there is a suspected new, temporary and reversible cause of hyponatremia based on clinical assessment (other than the administration of double-blind study medication):
 - Double-blind study medication will continue to be withheld.
 - The suspected cause of hyponatremia should be identified and corrected.
 - Serum sodium should be re-tested within one week after the first repeat:
 - If the repeat of serum sodium, obtained within one week after the first repeat, is < 130 mEq/L (130 mmol/L):
 - The subject must be immediately discontinued from the study, the Sponsor notified and the Day 14/ET visit performed. The Investigator will follow the subject until the event has resolved or stabilized.

dapagliflozin	MB102072
BMS-512148	Clinical Protocol

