3.5.5 Discontinuation Guidelines due to Elevated Creatine Kinase

Subjects with a CK > 10X ULN will have double-blind study medication withheld and a confirmatory, repeat CK, drawn upon receipt of the initial laboratory result (within 24 hours as much as possible and no later than within 3 days following receipt of the initial laboratory result).

- If the repeat CK is \leq 10X ULN, double-blind study medication may be resumed unless otherwise contraindicated
- If the repeat CK is > 10X ULN, the subject must be immediately discontinued from the study, the Sponsor notified and the Day 14 visit performed. The Investigator will follow the subject until the event has resolved or stabilized.

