4 TREATMENTS

All protocol-specified investigational and noninvestigational products are considered study drug.

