4.1.2 Noninvestigational Product

Other medications used as support or escape medication for preventative, diagnostic, or therapeutic reasons, as components of the standard of care for a given diagnosis, may be considered as noninvestigational products.

In this protocol, noninvestigational product is insulin.

All Insulin medication will be commercially available and will not be provided by the Sponsor and must continue to be taken at a stable effective therapeutic dose in accordance with the protocol, as applicable.

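### Section 5.3.9 orders a hold of study drug in upper tract UTI or urosepsis, and the protocol's own definition of that term includes insulin

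*Protocol*

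**What the plan says.** Section 5.3.9 gives guidance on urinary and genital infections. For the serious end of that range it states: "Study drug should be held in subjects with clinical evidence of upper tract UTI (eg pyelonephritis) or presumed urosepsis". The hold runs until the infection has been treated and the subject has recovered clinically. Nothing in the section says which product is meant.

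The term is defined in section 4: "All protocol-specified investigational and noninvestigational products are considered study drug". Section 4.1.2 completes the definition: "In this protocol, noninvestigational product is insulin". The same section says of insulin that it "must continue to be taken at a stable effective therapeutic dose in accordance with the protocol", and closes that sentence with the qualifier *as applicable*. Section 1.5, on risk and benefit in type 1 diabetes, says that "insulin treatment is required for survival and dapagliflozin would not be a replacement for insulin therapy".

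Three other rules in the protocol call for a temporary hold, and all three name the blinded product:

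- Creatinine, section 3.5.2: "Subjects will have double blind study medication withheld".
- Sodium, section 3.5.4: "will have double-blind study medication withheld and a confirmatory, repeat serum sodium".
- Creatine kinase, section 3.5.5: "will have double-blind study medication withheld and a confirmatory, repeat CK".

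**The concern.** A hold rule has to say exactly what is held. Here the term chosen is a defined one, and its definition takes in insulin. Applied as written, the instruction withholds insulin from subjects whom section 1.5 describes as absolutely insulin deficient, at a time of acute infection, and keeps it withheld until recovery.

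The triggering event is not remote. Section 1.4 reports a generally higher frequency of urinary tract infection with dapagliflozin, genitourinary infection is part of the primary endpoint in section 8.3, and this is the first study of the drug in type 1 diabetes. What is at stake is the clarity of a safety instruction. No estimate or analysis depends on it.

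**Working it through.** No arithmetic applies beyond a count. The check is to follow the term through the document and compare this rule with its parallels.

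**1. The definition.** Section 4 puts investigational and noninvestigational products together under *study drug*. Section 4.1.2 identifies the noninvestigational product as insulin. So *study drug* includes insulin by stated definition, without inference.

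**2. The instruction.** Section 5.3.9 uses that term. Neither the hold sentence nor the rest of the section limits it to dapagliflozin or placebo, and the section does not say that insulin continues.

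**3. The conflict.** Substituting the definition gives a hold on insulin. Section 4.1.2 says insulin is to go on being taken, and section 1.5 says subjects need it to survive. The section 4.1.2 sentence is qualified by accordance with the protocol and by applicability. That makes the clash with it less strict, but it also makes the sentence a weaker safeguard, because a hold ordered in section 5.3.9 is itself part of the protocol. Section 1.5 carries no such qualifier.

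**4. The parallel rules.**

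| Temporary-hold rule | Trigger | Product named |
|---|---|---|
| 3.5.2 | Serum creatinine | Double-blind study medication |
| 3.5.4 | Serum sodium | Double-blind study medication |
| 3.5.5 | Creatine kinase | Double-blind study medication |
| 5.3.9 | Upper tract UTI or presumed urosepsis | Study drug |

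Three of the four rules name the blinded product, and one does not. The narrower wording was available and in regular use.

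**5. How the term is used elsewhere.** It is used in two ways.

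- *Tablets only:* sections 3.2 (supply after the study), 4.2 (kits), 6.2.1 (start of nonserious adverse event collection) and 9.2.2 (drug records). Section 6.2.1 cannot mean insulin, because section 3.3.1 requires at least 12 months of insulin use before entry.
- *Consistent with the broad definition:* section 4.6.1, which covers drug sourced by the investigator and mentions vials and syringes, and section 4.6.2, which limits returns to drug that the sponsor supplied. The tablets come from the sponsor in bottles (Table 4.1), and insulin does not come from the sponsor (section 4.1.2).

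Usage elsewhere points to the tablets as the intended meaning in section 5.3.9, but it does not settle the wording.

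**The case against.** The strongest reply is that no competent reader would stop insulin, and that the protocol gives enough signals to prevent it.

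- Insulin has its own governing text. Section 4.1.2 has it continue, section 4.3 sends the reader to section 5 for insulin guidance, and section 5.3.6 gives unexpected hypoglycemia and hyperglycemia as the two main scenarios for adjusting it. Infection is not one of them.
- Section 3.5, the general stopping rule, separates the two products: investigational product must stop, and noninvestigational product is left to the investigator. It does not govern temporary holds, but it shows how the protocol treats insulin when treatment ends.
- Section 5.3.9 says it does not replace clinical judgment, and the sentence before the hold leaves decisions on therapy to judgment and local standards.
- The evidence for the broad usage is thin. The vials and syringes in section 4.6.1 stand in a section that also mentions cytotoxics and biologics, which reads like standard disposal text.
- If a term is used in two ways, its source is the definition in section 4, so editing section 5.3.9 alone leaves the other departures from the definition in place.

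Most of this stands as evidence of intent, and it is why the point is rated no higher than minor. None of it limits the term in the sentence that orders the hold. The last point is fair as editing advice, but the departures in sections 3.2, 4.2, 6.2.1 and 9.2.2 carry no comparable safety consequence, and the edit to section 5.3.9 repairs the sentence that matters.

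**Conclusion.** The concern holds. As written, and by the protocol's own definition, section 5.3.9 withholds insulin in upper tract UTI or presumed urosepsis, contrary to sections 1.5 and 4.1.2. It is an internal inconsistency in a safety instruction, and it is minor.

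The only count that bears on it is that one of four temporary-hold rules uses the wider term. The protocol gives no figure from which a chance of insulin being withheld could be computed, and none is claimed. In practice that is very unlikely. Endpoints, sample size and analyses are unaffected. The conclusion rests on the text alone and needs no assumption about rates.

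**What to change.** In section 5.3.9, replace *study drug* in the hold sentence with *double-blind study medication*, the term used in sections 3.5.2, 3.5.4 and 3.5.5. Add a clause stating that insulin is continued and adjusted as described in section 5.3.6.

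The cost is one phrase and one clause. No subject numbers, visits, procedures, forms or analyses change. Tightening the definition in section 4 as well would tidy the remaining usage, but the safety point does not need it.
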